4.1.2. Phase 3 Part

4.1.2.1 Primary Objective

The primary objective* of the Phase 3 part of this study is to assess the effect of RAD011 on hyperphagia-related behavior in patients with PWS.

*The Phase 3 part of the study will include all patients from the Phase 2 part of the study who were treated with dose level(s) selected for development in the Phase 3 part of the study.

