5. INVESTIGATIONAL PLAN

5.1. Overall Study Design

This is a seamless Phase 2/3, double-blind, randomized, placebo-controlled clinical study in patients diagnosed with PWS. Following consent (or legal guardian consent and patient assent as appropriate), patients will be screened for eligibility to participate in this study.

The Phase 2 portion of the study is to assess safety and tolerability. Dose safety and tolerability decisions will be made in Phase 2. All patients randomized to placebo and to the selected dose level(s) for Phase 3 evaluation will be included in the Phase 3 efficacy evaluation.

The study will consist of the following six similar periods for Phase 2 and Phase 3 of the study:

1. Screening Period (3 weeks)
 - a. Review of eligibility prior to proceeding to the Tolerability Period
2. Tolerability Period (6 weeks)

- a. Determination of randomization eligibility[†]
3. Dose Escalation Period (3 weeks)
4. Maintenance Period (24 weeks)[‡]
5. Taper Period (2 weeks)[‡]
6. Follow-Up Period (2 weeks)[‡].

[†]Patients who do not meet criteria for randomization eligibility will not be randomized to study SCOUT-015.

[‡]All patients participating in the Maintenance Period may be offered participation in the long-term extension study (SCOUT-016). Patients who do not enroll in the SCOUT-016 study will have their IP tapered over 2 weeks (14 days), followed by a 2-week (14-day) safety follow-up.

After approximately 45 patients complete 4 weeks of the Maintenance Period of the Phase 2 part of the study, the Data Monitoring Committee (DMC) will meet to review safety and tolerability data and to recommend 1 or 2 RAD011 dose level(s) for evaluation in the Phase 3 part of the study. Details regarding the dose selection for the Phase 3 part of the study will be described in the DMC charter.

A schematic overview of the study is presented in [Figure 2](#) for the Phase 2 part, and in [Figure 3](#) for the Phase 3 part.

Screening Period (3 weeks, Visit 1 [Weeks -3 to 0])

Phase 2 and Phase 3 of the study

All patients with a signed informed consent/assent will undergo Screening assessments. Screening assessments will include a full medical history and physical exam, a review of documentation of PWS diagnosis, an ECG, laboratory assessments, and questionnaires (including the HQ-CT) as described in [Section 5.8.2](#). To be eligible for the Tolerability Period, patients must meet the following criterion:

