Following review of Phase 2 safety and tolerability data by the DMC ([Section 10.4](#)), 1 or 2 dose level(s) will be recommended for further development and assessment in Phase 3 of the study. Therefore, following the Tolerability Period, patients meeting randomization eligibility criteria will be randomized in a way to obtain a balanced number of patients on RAD011 and placebo to receive double-blind treatment with Investigational Product (IP) at dose levels recommended by the DMC. Additional details are provided in [Section 7.5](#).

Dose Escalation Period (3 weeks, Visits 5 to 7 [Weeks 7 to 9])

Phase 2 of the study

After completing the Screening and Tolerability Periods, all randomized patients will be initiated on IP (RAD011 or placebo) 10 mg/kg/day (0.1 mL/kg/day) for a period of 1 week at Visit 5 (Week 7). Patients randomized to low dose or low volume IP (10 mg/kg/day) will continue at a dose of 10 mg/kg/day (0.1 mL/kg/day) until the end of Visit 7 (Week 9). Patients randomized to mid dose or mid volume IP (20 mg/kg/day) will have their dose increased to 20 mg/kg/day (0.2 mL/kg/day) at Visit 6 (Week 8) and will continue at that dose until the end of Visit 7 (Week 9). Patients randomized to high dose or high volume IP (40 mg/kg/day) will have their dose increased to 20 mg/kg/day (0.2 mL/kg/day) at Visit 6 (Week 8) and to 40 mg/kg/day (0.4 mL/kg/day) at Visit 7 (Week 9).

Details of the dose escalation schema are provided in [Table 4](#). Patients' weight at Visit 5 (Last Tolerability Period visit / first Dose Escalation Period visit) will be used to determine the

patient's actual doses (mL/day) to be administered from Visit 5 (Week 7) through completion of the maintenance phase Visit 14 (Week 34).

The Investigator, or designee, will contact patients/caregivers by phone call, video call, email, or other remote means of communication at Visits 6 (Week 8) and 7 (Week 9) to determine if the patient's dose may be escalated to the next dose level. Dose reductions will not be allowed during the Dose Escalation Period. If a patient cannot be escalated to the next dose level, the patient will be discontinued from the study.

Phase 3 of the study

After completing the Screening and Tolerability Periods, all patients will be initiated on 10 mg/kg/day IP (0.1 mL/kg/day) for a period of 1 week at Visit 5 (Week 7).

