5.2. Scientific Rationale for Study Design

Despite a large safety database with a well-characterized safety profile and dose-response relationship of EPIDIOLEX in multiple indications, data on safety and efficacy of CBD remains limited in patients with PWS. However, as PWS is a rare disease with significant unmet needs, multiple large-scale studies would be impractical and may delay access to efficacious therapies.

Therefore, this study is designed as a seamless Phase 2/3 study to assess safety and tolerability of multiple candidate doses in Phase 2 of the study (10 to 40 mg/kg/day), followed by Phase 3 of the study. In Phase 3 of the study, 1 or 2 candidate dose level(s) will be recommended by the DMC for further development and assessment based on safety and tolerability data. This approach will allow a streamlined way to confirm the safety and tolerability profile of RAD011 in patients with PWS while limiting the number of patients exposed to lesser tolerated doses. In addition, data from patients who participated in Phase 2 of the study in the dose group(s) chosen for continued development and assessment in Phase 3 of the study will contribute to the overall intent-to-treat (ITT) population. This, in turn, allows for more efficient recruitment in this rare disease population.

The double-blind design will minimize patient and Investigator bias, whereas the placebo control will allow better delineation of efficacy and safety profiles of RAD011. The use of placebo groups in this study is acceptable as there are no FDA approved treatments for hyperphagia in patients with PWS. In addition, the IP will be administered in addition to standard of care therapy, which can include GH supplementation and any additional behavioral interventions that have been implemented and maintained stable throughout the study.

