11.4. Statistical Analyses

11.4.1. Populations for Analyses

The following patient populations will be defined for analysis:

- Safety Population: the Safety Population will include all randomized patients who were treated with at least one dose of IP

- Intent to Treat (ITT) Population: the ITT Population will include all randomized patients
- Modified ITT (mITT) Population: the mITT Population will include all patients aged ≥ 12 years who were randomized, received at least 1 dose of IP, had at least 1 post-randomization HQ-CT questionnaire completed, and were randomized to receive the dose level(s) recommended for development in Phase 3 of the study, including patients in the Phase 2 part of the study who received the chosen dose level(s)
- Per Protocol (PP) Population: the PP Population will include all patients aged ≥ 12 years who were randomized, received at least 1 dose of IP, completed Week 34 without significant protocol deviations that were prospectively defined to impact efficacy (see SAP) and received the dose level(s) recommended for development in Phase 3 of the study, including patients in Phase 2 of the study who received the chosen dose level(s)
- Pharmacokinetic Evaluable Population: the PK Evaluable Population will include all patients who received at least 1 dose of IP and underwent at least 1 PK sample collection.

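### Phase 2 carry-over into the primary analysis is worded by dose received in some places and by dose randomized in others; the former could drop active patients who stopped before reaching their assigned dose

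*Protocol*

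**What the plan says.** Two rules for bringing Phase 2 patients into the Phase 3 evaluation appear in the protocol.

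By dose taken:
- The footnote to the Phase 3 primary objective (section 4.1.2.1), repeated for the secondary and other objectives (4.1.2.2, 4.1.2.3), includes "all patients from the Phase 2 part of the study who were treated with dose level(s) selected for development in the Phase 3 part".
- The last clause of the mITT definition (section 11.4.1, and the Synopsis) reads "including patients in the Phase 2 part of the study who received the chosen dose level(s".
- The per-protocol definition asks that patients "received the dose level(s) recommended for development in Phase 3 of the study".

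By dose assigned:
- Section 5.1: "All patients randomized to placebo and to the selected dose level(s) for Phase 3 evaluation will be included in the Phase 3 efficacy evaluation".
- Section 5.2 says that Phase 2 patients "in the dose group(s) chosen for continued development and assessment in Phase 3 of the study will contribute to the overall intent-to-treat (ITT) population".
- The main clause of the same mITT sentence asks that patients "were randomized to receive the dose level(s) recommended for development in Phase 3 of the study".
- Section 11.1 counts the Phase 2 patients who are not carried over by the dose to which they were randomized.
- Section 11.4.2 analyses the mITT population under a treatment-policy estimand, with randomization assignment as a fixed effect.

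Dose assigned and dose taken are not the same thing in the first weeks. Section 5.1 says that "all randomized patients will be initiated on IP (RAD011 or placebo) 10 mg/kg/day (0.1 mL/kg/day) for a period of 1 week at Visit 5". The low-dose arm stays at that level. The mid-dose arm moves to 20 mg/kg/day at Week 8. The high-dose arm moves to 20 at Week 8 and to 40 at Week 9 (Table 4).

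**The concern.** Reaching the assigned dose is a post-randomization event, and in this design it depends on tolerating the escalation. If Phase 2 patients enter the primary analysis only when they received the selected dose, those randomized to it who stopped earlier are left out of the active arm. Section 5.1 keeps placebo patients as randomized, so there is no matching exclusion on the control side. A patient in the same position who was enrolled during Phase 3 would stay in, because the as-received clause speaks only of Phase 2 patients. The comparison would then no longer be between the groups as randomized, and would not fit the treatment-policy estimand that section 11.4.2 names. Since the conflict sits inside the sentence that defines the primary population, it is more than a matter of footnotes.

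**Working it through.** **1. The plan's own figures.** Inputs from section 11.1: 50 per arm, difference 5, SD 7, 15% dropout.

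- Standard error = 7 × √(2/50) = 1.4, so 5/1.4 = 3.57.
- Two doses, two-sided 0.025: normal approximation 90.8%, noncentral t 90.0% (stated 90%).
- One dose, two-sided 0.05: 94.6% and 94.3% (stated 94%).
- 150/0.85 = 176.5 (stated 176); 100/0.85 = 117.6 (stated 118); 50/0.85 = 58.8 (stated about 59; the two-dose paragraph of section 11.1 says about 60).
- 176 + 15 = 191 and 118 + 30 = 148, as stated.

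All reproduce, and none of them changes with the carry-over wording.

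**2. Size of the group concerned.** About 45 Phase 2 patients (section 10.4), if split exactly 2:2:2:1:1:1 (section 7.5), give 45 × 2/9 = 10 per active dose. (Section 11.1 counts 15 for an unselected dose. With 45 patients that figure is reached only by adding the 5 matching-volume placebo patients, whom section 5.1 keeps. This is a separate count to reconcile.)

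**3. Where the two rules differ.** Take Phase 2 patients with at least one dose and one post-randomization HQ-CT:

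| Patient | By randomized dose | By dose received |
|---|---|---|
| Low arm, 10 mg/kg/day selected | in | in |
| Mid arm, 20 selected, stopped in Week 7 | in | out |
| High arm, 40 selected, stopped in Week 7 or 8 | in | out |
| Mid or high arm, assigned dose selected and reached | in | in |
| Placebo, stopped at any time | in (section 5.1) | not addressed |

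**4. Can rows two and three occur within mITT?** The first scheduled post-randomization HQ-CT is Visit 8 (Week 10), after escalation. Section 5.7.1 withdraws patients who cannot tolerate escalation. But section 6.3.1 has patients who stop investigational product without withdrawing consent continue on the planned schedule, and asks those unwilling or unable to do so for the Visit 14 assessments. Section 6.3.3 encourages the same assessments from those who withdraw consent. Table 7 labels Visit 14 as also the early-termination visit, and HQ-CT is among its assessments (section 5.8.5.1). So such patients can have the required score.

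**5. Size of the shift.** Assume *k* such patients in an arm of 59, with no benefit over placebo, and the planned 5-point benefit in the rest. With them the mean benefit is 5 × (59 − *k*)/59. Without them it is 5. The difference is 5*k*/59:

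- *k* = 1: 0.08 points
- *k* = 2: 0.17 points
- *k* = 3: 0.25 points

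The largest of these is 0.25/1.4 = 0.18 of the standard error above. The range of *k* (1 to 3 of 10) is an assumption; the protocol gives no rate of early stopping during escalation.

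**The case against.** The mITT definition is a list of conditions, one of which is randomization to a selected dose. The clause about Phase 2 patients is subordinate: it says that they count too, and a phrase that begins with *including* need not exclude anyone. Sections 5.1, 5.2, 11.1 and 11.4.2 all point the same way, and the footnotes belong to objectives, not to an analysis-set definition. Most patients who leave during escalation would have no post-randomization HQ-CT and fall outside mITT under either rule. The largest shift computed is under a fifth of a standard error.

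Most of this stands. It settles the intent and keeps the point small. It does not remove the conflict: the clause describes the Phase 2 members of the primary population by what they received, the footnotes use that rule alone, and the patients in step 4 are treated differently by the two.

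A reader might go further and infer that patients randomized to higher doses would be moved into a lower-dose arm because they passed through that level. Counted literally, 30 active Phase 2 patients were treated with 10 mg/kg/day, and 20 with 20 mg/kg/day, against 10 randomized to each. The documents do not support that inference. The mITT main clause requires randomization to the selected dose, and the model groups patients by randomization assignment. The literal footnote would also leave out every Phase 2 placebo patient, which cannot be meant. Nor do all arms pass through lower doses: the low-dose arm does not escalate.

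**Conclusion.** The carry-over rule contradicts itself, and the contradiction reaches the primary analysis population. Selection by randomized dose is evidently intended. The remaining risk is narrow: exclusion of Phase 2 patients randomized to a selected dose of 20 or 40 mg/kg/day who stopped before reaching it but have post-randomization HQ-CT data. That would favour the active arm by about 0.08 to 0.25 points, assuming one to three such patients with no benefit, an arm of about 59 and the planned 5-point effect in the rest. If 10 mg/kg/day is the only dose selected, this exclusion cannot arise, because every low-arm patient who took a dose received that level. It would be wrong to conclude that the plan as a whole breaks randomization or that its power, alpha or sample size is affected. The point is worth correcting because a choice between the two rules made after unblinding would be open to challenge.

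**What to change.** - In the footnotes to sections 4.1.2.1, 4.1.2.2 and 4.1.2.3, replace *who were treated with* by *who were randomized to placebo or to*.
- In the Phase 2 clause of the mITT definition (Synopsis and section 11.4.1), replace *who received the chosen dose level(s)* by *who were randomized to placebo or to the chosen dose level(s)*. The main clause does not name placebo either and can take the same words.
- Add one sentence: patients are analysed in their randomized arm whatever dose they reached.
- The per-protocol definition may stay conditional on treatment received, since that is its purpose.

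The cost is wording only. Design, sample size, alpha and model stay as they are. The change should be made before unblinding.

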4.1.2.2 Secondary Objectives

The secondary objectives* are to assess the following:

- Effect of RAD011 on irritability
- Effect of RAD011 on Clinician Global Impression of Change (CGI-C) in Hyperphagia
- Effect of RAD011 on Clinician Global Impression of Severity (CGI-S) of Hyperphagia
- Safety and tolerability of RAD011.

*The Phase 3 part of the study will include all patients from the Phase 2 part of the study who were treated with dose level(s) selected for development in the Phase 3 part of the study.

4.1.2.3 Other Objectives

The other objectives* of this study are to assess the:

- Effect of RAD011 on Caregiver Global Impression of Change (CaGI-C) in Hyperphagia
- Effect of RAD011 on Caregiver Global Impression of Severity (CaGI-S) of Hyperphagia
- Effect of RAD011 on Caregiver Global Impression of Change (CaGI-C) in Irritability
- Effect of RAD011 on overall behavior
- Effect of RAD011 on sleep
- Effect of RAD011 on body mass index (BMI) and weight
- Effect of RAD011 on skin-picking behavior
- Effect of RAD011 on total muscle/fat composition (performed at selected US sites).

*The Phase 3 part of the study will include all patients from the Phase 2 part of the study who were treated with dose level(s) selected for development in the Phase 3 part of the study.

5. INVESTIGATIONAL PLAN

5.1. Overall Study Design

This is a seamless Phase 2/3, double-blind, randomized, placebo-controlled clinical study in patients diagnosed with PWS. Following consent (or legal guardian consent and patient assent as appropriate), patients will be screened for eligibility to participate in this study.

The Phase 2 portion of the study is to assess safety and tolerability. Dose safety and tolerability decisions will be made in Phase 2. All patients randomized to placebo and to the selected dose level(s) for Phase 3 evaluation will be included in the Phase 3 efficacy evaluation.

The study will consist of the following six similar periods for Phase 2 and Phase 3 of the study:

1. Screening Period (3 weeks)
 - a. Review of eligibility prior to proceeding to the Tolerability Period
2. Tolerability Period (6 weeks)

- a. Determination of randomization eligibility[†]
3. Dose Escalation Period (3 weeks)
4. Maintenance Period (24 weeks)[‡]
5. Taper Period (2 weeks)[‡]
6. Follow-Up Period (2 weeks)[‡].

[†]Patients who do not meet criteria for randomization eligibility will not be randomized to study SCOUT-015.

[‡]All patients participating in the Maintenance Period may be offered participation in the long-term extension study (SCOUT-016). Patients who do not enroll in the SCOUT-016 study will have their IP tapered over 2 weeks (14 days), followed by a 2-week (14-day) safety follow-up.

After approximately 45 patients complete 4 weeks of the Maintenance Period of the Phase 2 part of the study, the Data Monitoring Committee (DMC) will meet to review safety and tolerability data and to recommend 1 or 2 RAD011 dose level(s) for evaluation in the Phase 3 part of the study. Details regarding the dose selection for the Phase 3 part of the study will be described in the DMC charter.

A schematic overview of the study is presented in [Figure 2](#) for the Phase 2 part, and in [Figure 3](#) for the Phase 3 part.

Screening Period (3 weeks, Visit 1 [Weeks -3 to 0])

Phase 2 and Phase 3 of the study

All patients with a signed informed consent/assent will undergo Screening assessments. Screening assessments will include a full medical history and physical exam, a review of documentation of PWS diagnosis, an ECG, laboratory assessments, and questionnaires (including the HQ-CT) as described in [Section 5.8.2](#). To be eligible for the Tolerability Period, patients must meet the following criterion:

- Mean HQ-CT score ≥ 13 obtained from HQ-CT scores as defined in [Section 6.4](#).

Patients not meeting Inclusion/Exclusion criteria for entry in the study will not be eligible for the study and may not be screened again. Caregivers will be required either to assist the patient or complete the questionnaires on behalf of the patient. The same caregiver should be available throughout the study to help in completing the questionnaires for purposes of consistency.

Tolerability Period (6 weeks, Visits 2 to 5 [Weeks 1 to 7])

Phase 2 and Phase 3 of the study

Patients who meet the eligibility criteria will undergo a 6-week Tolerability Period. During this Period, all patients will receive placebo at a dose of 0.1 mL/kg/day to assess tolerability of the formulation without active CBD and give patients time to adjust to study procedures and future

IP administration. Patients unable to tolerate the 0.1 mL/kg/day dose level will be withdrawn from the study.

Patients/caregivers will also complete serial HQ-CT questionnaires at 2-week intervals. At the end of the 6-week Tolerability Period and prior to randomization, patient randomization eligibility based on tolerability and HQ-CT scores will be evaluated. To be eligible for randomization, patients must meet both of the following HQ-CT criteria:

- Mean HQ-CT score ≥ 13 obtained from HQ-CT scores as defined in [Section 6.4](#)
- Decrease from the Tolerability Period to the Screening Period in HQ-CT score ≤ 7 points as defined in [Section 6.4](#).

Patients who do not meet criteria for randomization eligibility will not be randomized to study SCOUT-015.

Randomization (Visit 5 [Week 7])

Phase 2 of the study

Following the Tolerability Period, patients meeting randomization eligibility criteria will be randomized to 1 of 6 groups (3 active to 3 placebo with the ratio of 2:2:2:1:1:1): low dose (10 mg/kg/day [0.1 mL/kg/day]) RAD011, mid dose (20 mg/kg/day [0.2 mL/kg/day]) RAD011, high dose (40 mg/kg/day [0.4 mL/kg/day]) RAD011, low volume (0.1 mL/kg/day) placebo, mid volume (0.2 mL/kg/day) placebo, or high volume (0.4 mL/kg/day) placebo divided in two daily doses. Additional details are provided in [Section 7.5](#).

Phase 3 of the study

Following review of Phase 2 safety and tolerability data by the DMC ([Section 10.4](#)), 1 or 2 dose level(s) will be recommended for further development and assessment in Phase 3 of the study. Therefore, following the Tolerability Period, patients meeting randomization eligibility criteria will be randomized in a way to obtain a balanced number of patients on RAD011 and placebo to receive double-blind treatment with Investigational Product (IP) at dose levels recommended by the DMC. Additional details are provided in [Section 7.5](#).

Dose Escalation Period (3 weeks, Visits 5 to 7 [Weeks 7 to 9])

Phase 2 of the study

After completing the Screening and Tolerability Periods, all randomized patients will be initiated on IP (RAD011 or placebo) 10 mg/kg/day (0.1 mL/kg/day) for a period of 1 week at Visit 5 (Week 7). Patients randomized to low dose or low volume IP (10 mg/kg/day) will continue at a dose of 10 mg/kg/day (0.1 mL/kg/day) until the end of Visit 7 (Week 9). Patients randomized to mid dose or mid volume IP (20 mg/kg/day) will have their dose increased to 20 mg/kg/day (0.2 mL/kg/day) at Visit 6 (Week 8) and will continue at that dose until the end of Visit 7 (Week 9). Patients randomized to high dose or high volume IP (40 mg/kg/day) will have their dose increased to 20 mg/kg/day (0.2 mL/kg/day) at Visit 6 (Week 8) and to 40 mg/kg/day (0.4 mL/kg/day) at Visit 7 (Week 9).

Details of the dose escalation schema are provided in [Table 4](#). Patients' weight at Visit 5 (Last Tolerability Period visit / first Dose Escalation Period visit) will be used to determine the

patient's actual doses (mL/day) to be administered from Visit 5 (Week 7) through completion of the maintenance phase Visit 14 (Week 34).

The Investigator, or designee, will contact patients/caregivers by phone call, video call, email, or other remote means of communication at Visits 6 (Week 8) and 7 (Week 9) to determine if the patient's dose may be escalated to the next dose level. Dose reductions will not be allowed during the Dose Escalation Period. If a patient cannot be escalated to the next dose level, the patient will be discontinued from the study.

Phase 3 of the study

After completing the Screening and Tolerability Periods, all patients will be initiated on 10 mg/kg/day IP (0.1 mL/kg/day) for a period of 1 week at Visit 5 (Week 7).

The dose escalation schema for the DMC-recommended Phase 3 dose level(s) will follow the same dose escalation schedule as in the Phase 2 part of the study. Details of the dose escalation schema are provided in [Table 4](#). Patients' weight at Visit 5 (Last Tolerability Period visit / first Dose Escalation Period visit) will be used to determine the patient's actual doses (mL/day) to be administered from Visit 5 (Week 7) through Visit 14 (Week 34).

The Investigator, or designee, will contact patients/caregivers by phone call, video call, email, or other remote means of communication at Visits 6 (Week 8) and 7 (Week 9) to determine if the patient's dose may be escalated to the next dose level. Dose reductions will not be allowed during the Dose Escalation Period. If a patient cannot be escalated to the next dose level, the patient will be discontinued from the study.

Maintenance Period (24 weeks, Visits 8 to 14 [Weeks 10 to 34])

Phase 2 and Phase 3 of the study

After completing the 3-week Dose Escalation Period, patients will enter the 24-week Maintenance Period. Patients' weight at Visit 5 (last Tolerability Period visit / first Dose Escalation Period visit) will be used to determine the patient's actual doses (mL/day) to be administered between Visits 8 (Week 10) and 14 (Week 34).

Some patients may have their dose adjusted based on tolerability during the Maintenance Period as detailed in [Section 5.7.2](#).

[figure not shown]
After completion of the Maintenance Period, patients may be offered the opportunity to enroll in the long-term extension study (SCOUT-016). Patients who do not elect to enroll will be tapered off the IP.

Taper Period (14 days, Visit 14 [Week 34]) and Follow-up Period (14 days, Visits 15 and 16 [Weeks 36 and 38])

Patients who do not enroll in the long-term extension study (SCOUT-016) will have their IP tapered off over 14 days according to the following schedule: the IP should be decreased by 50% during the first 7 days, followed by an additional 50% during the following 7 days and then discontinued. The taper schedule may be modified at the discretion of the Investigator but cannot

be extended to a total period lasting more than 14 days. A final follow-up will be conducted 2 weeks after the last dose of IP for patients who are tapered off as described in [Section 5.8.6](#).

[figure not shown]
Figure 2: Study Design Schematic – Phase 2 of the Study

Abbreviations: DMC = Data Monitoring Committee; FU = follow-up; LTE = long-term extension; RAND = randomization.

*Patients assigned to placebo will include low, mid, and high volume placebo to match active drug and will be combined for statistical analysis.

Figure 3: Study Design Schematic – Phase 3 of the Study

Abbreviations: FU = follow-up; LTE = long-term extension; RAND = randomization; TBD = to be determined.

* Patients assigned to placebo will be further broken down to achieve balanced exposure between placebo and RAD011 patients. Patients in the placebo group (matching volume) will be combined for statistical analysis.

